4.6.4. Pharmacodynamics

4.6.4.1. B Cells

For flow cytometry panel, the absolute count and relative count (i.e. as a percentage of the total lymphocyte population) will be summarized by treatment arm for baseline, all post-baseline visits during the Treatment Period, and Week 24 endpoint using descriptive statistics.

The change from baseline and the percent change from baseline to each post-baseline visit during the Treatment Period and Week 24 endpoint will be summarized for absolute and relative count. Note that the baseline count is defined as the average of the non-missing results on or prior to the date of the first injection of blinded study treatment, unless one is missing, in which case the non-missing result will be used. Unscheduled and repeated measurements will be included.

In addition, the mean absolute and relative counts during the Treatment Period will be presented graphically over time (in weeks) by treatment arm. Similarly, the mean percentage change from baseline in absolute and relative counts will be presented graphically over time (in weeks) by treatment arm.

The change from baseline to Weeks 12 and 24 endpoints in absolute count will also be plotted against the change from baseline to Weeks 12 and 24 endpoints in the following variables:

- ACR20, 50, DAS28-CRP, HAQ-DI.

Similar plots will be generated for T, NK cells and peripheral helper T cells.

The change from baseline to Weeks 12 and 24 endpoints in absolute count will also be plotted against the total number of treatment-emergent infectious adverse events during the Treatment Period. Treatment arms will be identified using different symbols in the scatter plots.

A by-patient listing of cytometry cell counts during the Treatment Period will be provided.

4.6.4.2. Serum Immunoglobulin (Ig) Levels and Cytokines

Serum Ig levels, including IgA, IgG and IgM, and cytokines will be summarized by treatment arm for baseline, all post-baseline visits, Week 24 endpoint, and both change from baseline and percent change from baseline to each post-baseline visit and Week 24 endpoint. Baseline is defined as the last non-missing result on or prior to the date of the first injection of study treatment.

The change from baseline in Ig levels and cytokines to each post-baseline visit will also be summarized by treatment arm and whether the patient has positive anti-drug antibodies (ADAs) (yes or no) at that visit.

For each parameter, the mean percentage change from baseline over time (in weeks) will be summarized graphically by treatment arm.

Shift tables will be produced showing the frequency and percentage of patients with a minimum post-baseline result during the Treatment Period in each relevant category, by treatment arm and baseline result. Such shift tables will be produced for the following parameters and categories:

- IgA: < LLN to $\geq 0.35\text{g/L}$, and $<0.35\text{g/L}$.
- IgG: < LLN to $\geq 2.82\text{g/L}$, and $<2.82\text{g/L}$.
- IgM: < LLN to $\geq 0.20\text{g/L}$, and $<0.20\text{g/L}$.

The change from baseline to Weeks 12 and 24 endpoints in Ig levels and cytokines will also be plotted against the change from baseline to Weeks 12 and 24 endpoints in the following variables:

- ACR20, ACR50, DAS28-CRP, HAQ-DI,

The change from baseline to Week 24 endpoint in Ig levels and cytokines will also be plotted against the total number of treatment-emergent infectious adverse events during the Treatment Period. Treatment arms will be identified using different symbols in the scatter plots.

A by-patient listing of serum Ig levels and cytokines during the Treatment Period will be provided.

4.6.4.3. RO, sPD-1 and Biomarkers

RO, sPD-1 and biomarkers will be summarized by treatment arm for baseline, all post-baseline visits, Week 24 endpoint, and both change from baseline and percent change from baseline to each post-baseline visit and Week 24 endpoint. Baseline is defined as the last non-missing result on or prior to the date of the first injection of study treatment.

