4.1. Overall Design

This is a Phase 2, proof-of-concept, placebo-controlled, double-blind, randomized study in adult participants with moderately to severely active RA who have had an inadequate response to csDMARDs, or to bDMARDs/tsDMARDs. Participants will be administered LY3462817 or placebo IV Q4W.

Screening Period (Visit 1, Days -42 to -1)

Participants will sign the informed consent document(s) at Visit 1, prior to completion of any procedures. Participants will be evaluated for study eligibility \leq 42 days prior to the baseline visit (Visit 2).

Period 1: Double-blind Treatment (Visits 2 to 6; 12 weeks)

At the baseline visit (Visit 2), participants who fulfill the eligibility criteria will be randomized to receive LY3462817 700 mg, LY3462817 300 mg, or placebo in an allocation ratio of 2:1:1.

The double-blind treatment period will establish the clinical efficacy and safety of LY3462817. The study will be evaluated for the primary objective at the end of the double-blind treatment period.

Period 2 (Visits 6 to 10; 12 weeks)

Data from a Study KDAC interim analysis that includes Week 12 data from participants in the KDAC 700-mg cohort, must be reviewed prior to a participant proceeding to Period 2 in Study KDAD.

At Week 14, participants will be evaluated for clinical benefit.

Participants assigned to LY3462817 at baseline, and achieving low disease activity (CDAI \leq 10) at Week 14 will continue to receive LY3462817 at the randomized dose through Week 24 to assess safety and tolerability and evaluate efficacy.

All other participants at Week 14, regardless of baseline treatment assignment, will stop study drug infusions and should receive standard of care treatment at the investigator's discretion.

Posttreatment Safety Follow-up Period (Visits V801 and 802; 12 weeks)

Following Period 2, participants will be followed posttreatment for 12 weeks to assess safety, study drug exposure, and clinical disease activity measures. Participants who discontinue the study intervention per Section 7 will have their last visit at 12 weeks from the last administration of the study intervention.

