2.1. Multiplicity Adjustment

This is a proof of concept study. No adjustments will be made to adjust the performed efficacy analysis for multiplicity.

3. Analysis Sets

The following analysis data sets are defined to estimate the estimands defined in the protocol and to address safety.

Analysis Data Sets	Description
Full Analysis Set (FAS) for the primary estimand and for the secondary estimand for the secondary objective	
• All participants randomly assigned to study intervention and who take at least 1 dose of study intervention. Participants will be included in the analyses according to the planned intervention• For participants who discontinue study intervention and/or receive rescue therapy, post-discontinuation or post-rescue observations will not be included.
Safety analysis set to be used for safety assessments	
• All participants who are exposed to study intervention. Participants will be included in the analyses according to the intervention they actually received.• All observed data will be included in the analysis set.
Pharmacokinetic(PK) analysis set to be used for PK assessments	
• All participants randomly assigned to study intervention and who take at least 1 dose of study intervention and have PK data available.• All observed data until discontinuation of intervention will be included in the analysis set.

4. Statistical Analyses

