4.6. Safety Analyses

The following safety measures will be summarized and analyzed using the Safety Analysis Set. Patients will be analyzed according to the treatment to which they were assigned. Safety summaries will be presented by treatment arm as follows: LY3462817 300 mg, LY 3462817 700 mg, All LY3462817, and Placebo. (Coming from CPT Section 9.4.5. Other Safety Analysis and 9.4.6 Other Analyses), information on this section will be copied from protocol, if needed; it can be edited and additional details may be added.

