4.6.1. Extent of Exposure

Duration of Exposure to Study Treatment

Duration of exposure on treatment (defined as time since first injection in days) during the Double-blind Treatment Period will be summarized by treatment arm and provided as listing. Duration of exposure on treatment will be calculated as:

(Date of last study visit during the Double-blind Treatment Period – Date of first injection + 1).

For patients who discontinue from the treatment, the date of discontinuation prior to Period 2 will be used.

Descriptive statistics for duration of exposure and the frequency and percentage of patients falling into the following ranges will be summarized: 0, >0, ≥ 7 days, ≥ 14 days, ≥ 30 days, ≥ 60 days, ≥ 84 days. The frequency and percentage of patients with duration of exposure in the following categories will also be summarized: 0 days, <14 days, ≥ 14 to <30 days, ≥ 30 to <60 days, ≥ 60 to <84 days, ≥ 84 days.

Overall exposure for each treatment arm will also be summarized in total patient years. This will be calculated as follows:

Exposure in patient years = Sum of duration of exposure (for all patients in treatment arm) / 365.25.

The analyses in Double-blind Treatment Period will be repeated for all visits in period 2 for subjects who remain on LY3462817 300 mg or LY3462817 700 mg.

Total Dose of Study Treatment

Total dose of active study treatment per subject will be summarized by active treatment arm using descriptive statistics. The total dose (mg) will be calculated as:

Total Dose = Sum over all injections received of [dose of LY (mg) prescribed per injection]

A by-patient listing of exposure duration and total dose will be provided.

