4.7. Other Analyses

4.7.1. Other variables and/or parameters

LY3462817 concentrations will be illustrated graphically and summarized descriptively. To facilitate the planning of future clinical studies, a model-based approach implemented using nonlinear mixed effects modeling (NONMEM) or other appropriate software may be conducted. Receptor occupancy and soluble PD-1 data over time will be summarized by dose level. Exploratory PK/PD analyses may be conducted to evaluate the relationship between LY3462817 exposure and selected measures of response (for example, RO, sPD-1, clinical endpoints, and/or biomarkers). As appropriate, data from the present study may be combined with data from other

studies in model-based analyses. Additional analyses may be conducted if deemed appropriate. Further details on PK and PK/PD analyses will be provided in the PK/PD analysis plan.

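### At Week 24 and later, the by-arm pharmacodynamic summaries pool participants still on LY3462817 with participants last infused at Week 12, so they cannot be read as on-dose target engagement

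*SAP*

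**What the plan says.** **Summary rule.** SAP 4.6.4.3 says "RO, sPD-1 and biomarkers will be summarized by treatment arm for baseline, all post-baseline visits, Week 24 endpoint". SAP 4.6.4.2 says "Serum Ig levels, including IgA, IgG and IgM, and cytokines will be summarized by treatment arm for baseline, all post-baseline visits, Week 24 endpoint". For flow cytometry, SAP 4.6.4.1 says that absolute and relative counts "will be summarized by treatment arm for baseline, all post-baseline visits during the Treatment Period, and Week 24 endpoint using descriptive statistics". SAP 4.7.1 adds that "Receptor occupancy and soluble PD-1 data over time will be summarized by dose level".

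**Data and grouping.** These sections (apart from 4.7.1) sit under SAP 4.6, which uses the Safety Analysis Set and says "Patients will be analyzed according to the treatment to which they were assigned". For that set, SAP Section 3 (Analysis Sets) says "All observed data will be included in the analysis set".

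**Plots.** SAP 4.6.4.1 and 4.6.4.2 also plan scatter plots of change in cells, immunoglobulins and cytokines against ACR20, ACR50, DAS28-CRP and HAQ-DI at Weeks 12 and 24.

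**Dosing in Period 2.** Protocol 4.1 continues LY3462817 through Week 24 only for participants randomised to it who have CDAI of 10 or less at Week 14. Everyone else "will stop study drug infusions and should receive standard of care treatment at the investigator's discretion". The schedule of activities (protocol 1.3) agrees. SAP 1.2, by contrast, has every participant receiving LY3462817 in Period 2.

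**A restriction the SAP makes elsewhere.** SAP 4.6.1 repeats the exposure analysis in Period 2 only "for subjects who remain on LY3462817 300 mg or LY3462817 700 mg".

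**The concern.** From Week 16 each active arm splits into two groups with different drug histories, and the split is decided by clinical response. The pharmacodynamic sections do not mention it. A Week 24 mean labelled 300 mg or 700 mg then describes neither group, and it moves with the share of participants who continued as well as with dose.

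Protocol 2.2 treats receptor occupancy (RO) and soluble PD-1 (sPD-1) together as measures of target engagement, and protocol 4.3 wants two dose levels partly to help project to later dose-ranging work. A reader could take a Week 24 fall as loss of engagement on a dose, or a Week 24 difference between arms as a dose effect, when either may reflect who was still being infused.

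The Week 24 plots have a related weakness. Continued dosing depends on CDAI, so drug exposure and the clinical outcome on the other axis are linked by design, and no symbol for dosing status is planned.

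**Working it through.** **1. Which visits are affected.** Reading the schedule of activities, with all samples taken before dosing:

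| Measure | Post-baseline visits up to Week 24 | Follow-up |
|---|---|---|
| RO | Weeks 2, 4, 8, 12, 24 | Weeks 28, 36 |
| sPD-1 | Weeks 2, 4, 8, 12, 16, 24 | Weeks 28, 36 |
| Cells (flow cytometry), cytokines | Weeks 4, 12, 16, 24 | Week 36 |
| Immunoglobulins | Weeks 12, 24 | Week 36 |

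No one stops under the Week 14 rule before Week 14, so Weeks 2 to 12 are clean. RO and immunoglobulins are not sampled at Week 16. The other Week 16 samples are pre-dose, 28 days after the Week 12 infusion in both groups, so drug history is the same. None of these measures is sampled at Week 20. Week 24 is thus the first visit where drug history differs.

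**2. The plan's own figure.** Protocol 2.2 gives clearance 10.9 mL/hr, volume 3.9 L and half-life of approximately 10 days. Check: ln 2 × 3900 / 10.9 = 248 h = 10.3 days. It reproduces.

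**3. Modelled pre-dose concentration.** One compartment with superposed doses: C = (Dose/V) × Σ 0.5^(days since dose / 10).

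- Continuers at Week 24 (doses 28, 56, 84, 112, 140 and 168 days earlier): sum = 0.1677.
- Stopped participants at Week 24 (doses 84, 112, 140 and 168 days earlier): sum = 0.00346.
- 700 mg: 700/3.9 = 179.5 mg/L, giving 30.1 versus 0.62 mg/L.
- 300 mg: 300/3.9 = 76.9 mg/L, giving 12.9 versus 0.27 mg/L.
- Ratio of stopped to continuing: 0.00346/0.1677 = 0.021. With a half-life of 10.3 days it is 0.023.
- Week 16: ratio 1.00.
- Week 12 pre-dose at 700 mg: 179.5 × 0.1672 = 30.0 mg/L, so on this model Week 12 already gives the on-dose trough.

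At Week 24, stopped participants are 84 days, about 8 half-lives, past the last infusion.

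**4. What pooling does to an arm mean.** If a share R of an arm continues, and all stopped participants are sampled, pooled/continuer = R + (1 − R) × 0.021. The documents give no value for R, so a range is assumed:

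| R | Pooled mean as % of continuer mean |
|---|---|
| 10% | 12% |
| 20% | 22% |
| 30% | 31% |
| 50% | 51% |

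If, say, R were 50% at 700 mg and 20% at 300 mg, the pooled concentration ratio between doses would be (700/300) × (0.510/0.216) = 5.5, against 2.3 on dose.

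These are serum concentrations. They show how unlike the pooled groups are in exposure; they are not estimates of RO, sPD-1 or cell counts.

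**The case against.** **These are descriptive tables, and a summary by assigned arm is correct as such.** This stands. A reader might infer that the trial's by-dose target-engagement estimate is wrong. The documents do not support that: Weeks 2 to 12 use the arms before the Week 14 stop, and they include the on-dose trough. The fault is confined to how Week 24 and later can be read.

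**A 49-fold concentration gap need not mean a large RO gap.** This also stands. Protocol 4.3 reports plasma receptor saturation at 350 and 700 mg for 4 weeks and longer, and is silent on 12 weeks. That occupancy will visibly fall, or that the arm with more responders will look better engaged, is possible but not shown.

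**The number of stopped participants sampled is unsettled.** This stands too. Protocol 7.2 has a participant who needs another effective RA agent leave the study before that agent starts, which does not fit the Week 14 move to standard of care in 4.1. Protocol 4.1 also ends follow-up 12 weeks after the last infusion for those who discontinue under Section 7. If that covers the Week 14 stop, their last visit would be at Week 24 (12 + 12). These passages must be reconciled. The fewer stopped participants sampled, the smaller the mixture.

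**Other text may already handle it.** Protocol 9.3 groups the safety population by intervention actually received within each period, SAP 4.1 presents Period 2 safety data separately, and PK/PD detail is left to another plan. But SAP 4.6 says assigned treatment, separating periods does not separate dosed from stopped participants, and the by-arm tables are commitments of the SAP itself.

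**The plots show individuals and omit RO and sPD-1.** True, so nothing is averaged there. Dosing status is still not marked, and it is tied to the clinical axis.

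**Conclusion.** The point holds for Week 24, and for later follow-up samples wherever all post-baseline visits are summarised. The arm-level RO, sPD-1, cell, immunoglobulin and cytokine results, and the Week 24 plots, cannot be read as on-dose engagement and depend partly on each arm's share of Week 14 responders. For measures that respond to other RA drugs, standard of care may add to the difference.

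The firm size is exposure: about 2% of the continuers' pre-dose concentration in stopped participants, given a one-compartment model with the protocol's volume and half-life. The RO difference, the share who continue and the number of stopped participants sampled are all unknown.

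A reader might extend this to Week 16. For drug exposure that is not supported; only standard of care begun from Week 14 could differ then. Nor does the point touch the Week 12 primary comparison.

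The likely source is SAP 1.2. The SAP is based on the protocol dated 05AUG2020, while the protocol supplied cites September 2020 data and so is later. If every participant were dosed in Period 2, this mix would not arise within an active arm. This is a cheap improvement, not a threat to the trial's conclusions.

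**What to change.** 1. Reconcile SAP 1.2 with the protocol's description of Period 2.
2. In SAP 4.6.4.1 to 4.6.4.3 and 4.7.1, present summaries and graphs at Week 24 and later by randomised dose and dosing status (continued LY3462817, or stopped after Week 12), with weeks since last infusion. Give the number sampled in each group.
3. Mark the same status on the Week 24 biomarker-versus-clinical plots.
4. State that the by-dose engagement comparison uses Weeks 2 to 12. Keep the Week 16 samples; they are valid 4-week troughs in both groups.

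The cost is SAP wording and one grouping variable, with no new data. The downside is smaller numbers per cell, from arms of about 20 and 40. Continuers are also selected on Week 14 response, so their 300 mg versus 700 mg contrast is descriptive, not randomised, and should be labelled so. For that reason, simply restricting Week 24 to continuers would not restore a dose comparison.

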4.6.4.4. Immunogenicity

The frequency and percentage of patients with positive anti-drug antibodies (ADAs) by visit will be summarized by treatment arm. The frequency and percentage of patients with positive ADAs

at any time point during the Treatment Period (including pre-treatment visits) up to and including Visit 9 (Week 24) will also be summarized by treatment arm.

The frequency and percentage of patients with a treatment-emergent positive ADA incidence will be summarized by treatment arm. A treatment-emergent incidence is defined as a four-fold increase [2 dilution increase] in immunogenicity titer over the baseline titer during the Treatment Period. Scheduled visits, unscheduled visits, and repeat measurements will be included.

The time to the development of treatment-emergent ADAs will be calculated as:

Time to development of treatment-emergent ADAs (in weeks) = (Date of development of treatment-emergent ADAs – Date of randomization + 1) / 7.

If a patient has not developed treatment-emergent ADAs, they will be censored at the date of the last immunogenicity assessment during the Treatment Period. If they did not have an immunogenicity assessment, they will be censored at the date of first injection.

The time to development of treatment-emergent ADAs will be analyzed using a Cox proportional hazards model, with treatment arm and strata (previous RA therapy population) fitted as explanatory variables. The estimated hazard ratio, 95% confidence interval and p-value for treatment comparisons between each LY dose and placebo will be presented. A Kaplan-Meier plot of the time to development of treatment-emergent ADAs will be presented by treatment arm.

The frequency and percentage of patients with both a treatment-emergent positive ADA incidence (yes, no) and at least one treatment-emergent Hypersensitivity adverse event (yes, no) will be summarized by treatment arm. Similarly, the frequency and percentage of patients with both a treatment-emergent positive ADA incidence (yes, no) and at least one treatment-emergent injection site reaction (yes, no) adverse event will be summarized by treatment arm.

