Study J1A-MC-KDAD	Screen	Period 1: Double-blind treatment					Period 2				ED	Post-treatment follow-up		Comments
Day ± Visit Tolerance	-42 to -1	1	14 ± 7	28 ± 7	56 ± 7	84 ± 7	98 ± 7	112 ± 7	140 ± 7	168 ± 7	Any	196 ± 7	252 ± 7	Visit 1 procedures may be conducted over more than 1 day as long as all tasks are completed within the tolerance window.
Week		-	2	4	8	12	14	16	20	24	-	28	36 or ETV + 12	
Visit number	V1	V2	V3	V4	V5	V6	V7	V8	V9	V10	ET	V801	V802	
Procedures														
Tuberculosis (TB) test	X													See Section 8.2.7 for details of TB testing. Participants will return 48 to 72 hours after a tuberculin test (TST) for their test results. If the QuantiFERON®-TB Gold test or T-SPOT® TB test is available, either test may be used instead of the PPD TB test. The QuantiFERON®-TB test is done centrally or locally; the T-SPOT® TB test must be done locally.
Human immunodeficiency virus (HIV) screening tests	X													
Hepatitis C virus (HCV) screening tests	X													
Hepatitis B virus (HBV) screening tests	X													Includes HBsAg and anti-HBc.
Hepatitis B virus (HBV) DNA	X					X				X	X		X	Any enrolled participant who is HBcAb+ will undergo monitoring of HBV DNA during the study treatment.
Flow cytometry panel		X		X		X		X		X	X		X	Includes: TBNK, collect prior to dosing
Cytokine panel		X		X		X		X		X	X		X	Collect prior to dosing

Study J1A-MC-KDAD	Screen	Period 1: Double-blind treatment					Period 2				ED	Post-treatment follow-up		Comments
Day ± Visit Tolerance	-42 to -1	1	14 ± 7	28 ± 7	56 ± 7	84 ± 7	98 ± 7	112 ± 7	140 ± 7	168 ± 7	Any	196 ± 7	252 ± 7	Visit 1 procedures may be conducted over more than 1 day as long as all tasks are completed within the tolerance window.
Week	-	2	4	8	12	14	16	20	24	-	28	36 or ETV + 12		
Visit number	V1	V2	V3	V4	V5	V6	V7	V8	V9	V10	ET	V801	V802	
Procedures														
Immunoglobulin panel		X				X				X	X		X	Includes: IgG, IgM, and IgA Collect prior to dosing
Pharmacokinetic samples		X	X	X	X	X		X		X	X	X	X	Collect prior to dosing
Immunogenicity samples		X		X		X		X		X	X	X	X	Collect prior to dosing
Receptor occupancy		X	X	X	X	X				X	X	X	X	Collect prior to dosing
Peripheral helper T cells		X	X	X	X	X				X	X	X	X	Collect prior to dosing
Stored samples														
Genetics sample		X												Collect prior to dosing
Exploratory biomarker samples		X	X	X	X	X	X	X		X	X		X	See Section 10.2 for details Collect prior to dosing
Randomization and dosing														
Randomization		X												

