8.9. Immunogenicity Assessments

All samples for immunogenicity should be taken predose when applicable at the visits and times specified in the SoA (Section 1.3). Venous blood samples will be collected and evaluated to determine antibody production against LY3462817. To interpret the results of immunogenicity, venous blood samples will be collected at the same time points to determine the concentrations of LY3462817. Antidrug antibodies may be further characterized for their ability to neutralize the activity of LY3462817.

Treatment-emergent antidrug antibody (TE-ADA) classifications are described in Section 9.4.6.

Sample retention is described in Appendix 1, Section 10.1.12.

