9.4.6. Evaluation of Immunogenicity

Treatment-emergent antidrug antibodies (ADAs) are defined as participants

- with a 2-fold (1 dilution) increase in titer than the minimum required dilution if no ADAs were detected at baseline (treatment-induced ADA) or

- with a 4-fold (2 dilutions) increase in titer compared with baseline if ADAs were detected at baseline (treatment-boosted ADA).

The frequency and percentage of participants with preexisting ADA and who are TE-ADA positive (TE-ADA+) to LY3462817 will be tabulated.

For the TE ADA+ participants, the distribution of maximum titers will be described. The frequency of neutralizing antibodies, if assessed, may also be tabulated for the TE-ADA+ participants.

The relationship between the presence of antibodies and LY3462817 concentrations and PD response, including safety and efficacy, may also be assessed. Additional details may be provided in the SAP.

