The baseline period is defined as Visit 1 through pre-dose Visit 2. The Double-blind Treatment Period starts after the first injection of study treatment at Visit 2 (Week 0) and ends on the date of Visit 6 (Week 12) or the early discontinuation visit. The Period 2 starts after the date of Visit 6 (Week 12) or the early discontinuation visit and lasts up to 24 weeks following the last injection of study treatment. Additional follow-up beyond 24 weeks may be deemed necessary and, if so, any data collected will be considered as part of Period 2.

Unless otherwise specified, baseline for the Treatment Period is defined as the last non-missing assessment on or prior to the date of the first injection of study treatment, scheduled to be given at the end of Visit 2. Any assessment collected after the first injection through the date of the Week 12 or early discontinuation visit is defined as post-baseline for the Treatment Period.

Data collected at early discontinuation visits will be mapped to the next planned visit number for that patient. For by-visit summaries, only visits in which a measure was scheduled to be collected will be summarized.

Summaries of safety data collected during Period 2 will be presented separately. Unless otherwise specified, follow-up baseline is defined as the last non-missing assessment on or prior to the date of Week 12 or the date of the early discontinuation visit.

Change from baseline will be calculated as the post-baseline value minus the baseline value. Percent change from baseline is defined as $(100 \times (\text{post-baseline} - \text{baseline}) / \text{baseline})$. If all baseline values are missing for a particular variable, the change from baseline and percent change from baseline will not be calculated.

The statistical analyses of efficacy, health outcomes, and safety measures will be performed using SAS Version 9.4 or higher. Lilly will be responsible for conducting analyses.

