4.6.2.6. Suicide-related Thoughts and Behaviors

Suicide-related ideations and behaviors, based on C-SSRS, will be summarized by treatment arm separately for patients who completed the C-SSRS starting at enrollment versus patients who were already enrolled when the C-SSRS was introduced to the study during the Treatment Period.

Treatment-emergent suicide-related ideations and behaviors during the Treatment Period are defined as any ideation or behavior reported after the baseline visit (Visit 2) and on or prior to Visit 10 (Week 24) or early discontinuation. The frequency and percentage of patients with treatment-emergent suicide-related ideations and behaviors will be summarized by treatment arm for patients who completed the C-SSRS starting at enrollment by C-SSRS category (1-10), by type (ideation or behavior) and overall during the Treatment Period.

Suicide-related ideations and behaviors will be listed by patient and visit separately for patients who completed the C-SSRS starting at enrollment versus patients who were already enrolled when the C-SSRS was introduced to the study. Only patients that show suicidal ideation/behavior will be displayed, including lifetime history at screening. If a patient answers are all 'no' for the C-SSRS, then that patient will not be displayed. However, if a patient reported any ideation or

behavior at any time point then all their ideation and behavior will be displayed, even if not positive.

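### The any-time ADA summary ends at a visit that does not exist (Visit 9 is Week 20, Week 24 is Visit 10), so its window depends on which half of the label is programmed

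*SAP*

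**What the plan says.** SAP 4.6.4.4 plans several ADA outputs. The first is positivity by visit, with no end stated. The second is the share of participants positive "at any time point during the Treatment Period (including pre-treatment visits) up to and including Visit 9 (Week 24"). The others are treatment-emergent ADA (TE-ADA), a time-to-TE-ADA analysis censored at the last assessment in the Treatment Period, and cross-tabulations of TE-ADA with hypersensitivity and injection-site reactions. These rest on TE-ADA, which is defined over the Treatment Period without naming a visit.

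The protocol's Schedule of Activities (1.3) lists the visits as "V1 V2 V3 V4 V5 V6 V7 V8 V9 V10 ET V801 V802". Visits 8, 9 and 10 fall on days "112 ± 7 140 ± 7 168 ± 7". Its row for "Immunogenicity samples" is marked at V2, V4, V6, V8, V10, ET, V801 and V802, and is blank at V9.

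Elsewhere the SAP pairs Week 24 with Visit 10. Section 4.6.2 does so for treatment-emergent adverse events, and 4.6.2.6 counts suicide-related events reported "on or prior to Visit 10 (Week 24) or early discontinuation".

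Protocol 9.4.6 sets no cut-off: "The frequency and percentage of participants with preexisting ADA and who are TE-ADA positive (TE-ADA+) to LY3462817 will be tabulated". Protocol 8.9 treats drug level as relevant to reading ADA results: "To interpret the results of immunogenicity, venous blood samples will be collected at the same time points to determine the concentrations of LY3462817".

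**The concern.** The label sets an operative analysis window, and its two halves name different visits. A programmer who filters on Visit 9 and one who filters on Week 24 will produce different tables from the same data, and both can cite the SAP.

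Neither version reaches the follow-up samples of a participant who completes the schedule. If TE-ADA is run over the longer Treatment Period of SAP 4.1, a participant first positive at V801 or V802 would count as TE-ADA positive yet appear negative in the any-time row of the same section. For participants dosed through Week 24, the excluded V802 sample is also the only one taken well clear of drug. That matters if circulating drug makes antibodies harder to detect.

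**Working it through.** **Step 1. Reproduce the label.** Days come from the Schedule of Activities. Visit 9 = 140 / 7 = Week 20. Visit 10 = 168 / 7 = Week 24. The pairing of Visit 9 with Week 24 does not reproduce.

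**Step 2. Count scheduled samples under each reading** (ET excluded, because a participant on the full schedule has none).

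| Visit | Day | Week | ADA sample | Cut at Visit 9 | Cut at Week 24 |
|---|---|---|---|---|---|
| V2 | 1 | baseline | yes | kept | kept |
| V4 | 28 | 4 | yes | kept | kept |
| V6 | 84 | 12 | yes | kept | kept |
| V8 | 112 | 16 | yes | kept | kept |
| V9 | 140 | 20 | no | – | – |
| V10 | 168 | 24 | yes | dropped | kept |
| V801 | 196 | 28 | yes | dropped | dropped |
| V802 | 252 | 36 | yes | dropped | dropped |
| Total | | | 7 | 4 of 7 | 5 of 7 |

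The Visit 9 cut ends in practice at Week 16, because V9 has no sample.

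**Step 3. Early terminators.** The Schedule of Activities places V802 at Week 36 or 12 weeks after the early termination visit. Termination at Week 4, 8 or 12 puts V802 at Week 16, 20 or 24, so a calendar cut at Week 24 keeps it. Termination at Week 16 gives Week 28, which is outside the cut.

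**Step 4. Drug remaining at each sample.** Protocol 2.2 gives a terminal half-life of about 10 days. Fraction of the last dose remaining = 2^(−days / 10).

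- 4 weeks after a dose: 2^(−28/10) = 0.144, about 14%.
- 12 weeks after a dose: 2^(−84/10) = 0.0030, about 0.3%.
- Check from the stated clearance and volume: 0.693 × 3900 mL / 10.9 mL/h = 248 h = 10.3 days, which gives 0.153 and 0.0036. The picture is unchanged.

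For a participant dosed through Week 24, V4 to V10 are pre-dose samples 4 weeks after the preceding dose, and V801 is also 4 weeks after a dose. Only V802 is 12 weeks after one. For an active-arm participant whose last dose was at Week 12 and who stays on the visit schedule, V8 is the 4-week sample and V10 the 12-week sample. The Visit 9 cut loses that 12-week sample; the Week 24 cut keeps it.

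**Step 5. What the other ADA outputs use.** They use the Treatment Period, whose end the SAP does not state consistently:

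- SAP 4.1 defines it as Period 1 plus Period 2, and Period 2 "lasts up to 24 weeks following the last injection of study treatment". That covers V801 and V802.
- SAP 4.6.2.1 describes it as planned for 24 weeks.
- SAP 4.6.2.3 names a separate Post-Treatment Follow-up Period.

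**The case against.** The strongest reply is that this is a one-digit slip with a clear intent. The SAP writes Visit 10 for Week 24 elsewhere, so a careful programmer would use Visit 10. Ending an any-time summary at the last on-treatment visit is a legitimate choice. Protocol 9.4.6 asks for preexisting ADA and TE-ADA, not for this summary, so no protocol requirement is breached. Much of this stands: the intended visit is probably Visit 10, and the any-time summary is the SAP's own addition. But the text still has to be corrected before it can be programmed without a guess, and the SAP does not say that an on-treatment figure is what it wants.

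A reader might infer three stronger things that the documents do not support.

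- *All follow-up ADA samples are lost.* The cap sits in one sentence. The by-visit table has no such limit, and a calendar Week 24 cut can keep early terminators' follow-up samples (Step 3).
- *TE-ADA and its cross-tabulations with hypersensitivity and injection-site reactions are understated because of this label.* They do not use it. Their uncertainty comes from the unsettled end of the Treatment Period, and under SAP 4.1 they include V801 and V802.
- *ADA positivity is necessarily understated because the dropped samples contain least drug.* Under the Week 24 reading, participants last dosed at Week 12 keep a sample taken 12 weeks after dosing. The direction of bias also presumes that residual drug hinders detection; protocol 8.9 makes that worth considering but gives no drug tolerance for the assay.

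**Conclusion.** The inconsistency is certain; its effect is confined to one table. The any-time ADA-positive summary keeps 4 or 5 of 7 scheduled samples, depending on which half of the label is followed. For full-schedule participants it omits V801 and V802 either way. The number of participants this would reclassify cannot be estimated from the documents. Any understatement rests on the assumption that residual drug interferes with the assay. The primary endpoint and the other efficacy analyses are untouched.

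The point is still worth correcting. The window cannot be programmed unambiguously as written, and the any-time row can disagree with TE-ADA in the same section. Changing the label alone would not settle the second problem, because the Treatment Period has no single end in the SAP.

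**What to change.** In SAP 4.6.4.4, replace the visit limit at the end of the any-time sentence with *up to and including the last follow-up visit (V802)*. Keep the parenthesis that includes pre-treatment visits: restricting the sentence to post-baseline samples would contradict it and change the quantity by removing baseline positives. State the same end of window for the TE-ADA count and for the censoring date in the time-to-TE-ADA analysis, rather than leaving both to the term Treatment Period. If an on-treatment figure is also wanted, add a column ending at Visit 10 (Week 24).

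The samples are already scheduled, so no data collection changes. The cost is a little SAP wording and programming, and the reported ADA frequency may be slightly higher.
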